5.2.4. Analysis of the secondary endpoints

The patient population in Spain will be characterised by describing the following variables:

- Age
- Sex
- CHA2DS2-VASc score
- HAS-BLED score
- Kidney function (creatinine clearance)
- Risk factors associated with stroke and/or haemorrhage in the medical history and baseline period
- Comorbidities
- Concomitant medication
- Duration of previous treatment with VKAs
- Reasons for changing the dose of Pradaxa® or discontinuing Pradaxa®/VKAs.
- Pradaxa® dose

5.2.6. Safety analysis

The safety analyses will include all patients participating in the study who actually receive follow-up (patients for whom we have follow-up data). The statistical analyses and reporting of AEs will be descriptive in nature, based on BI standards and will focus on adverse reactions to a medication (i.e., AEs related to the anticoagulant treatment).

The safety analysis will be based on the concept of adverse events that arise during treatment. AEs that worsen with the treatment will also be deemed to “arise during treatment”. AEs that appear before the first study visit or after the end of the 7-month follow-up period (the 6 months of the study + 30 days follow-up) will not be deemed to have arisen during treatment and will not be included in the summary tables.

The safety analyses will focus on the following parameters:

- Adverse reactions to the medication
- Adverse reactions to the medication that cause the anticoagulant treatment to be discontinued
- Serious adverse reactions to the medication

- Deaths
- SAEs

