5.2.3. Analysis of the primary endpoint

The description of patients' perception of their treatment for NVAf will be achieved using the PACT-Q2 questionnaire.

For this, comparisons of paired samples (Student's paired t-test or the non-parametric Wilcoxon signed-rank test for data without a normal distribution) will be used to compare the scores obtained in the final assessment (continuation period) to those from the baseline assessment. Additional comparisons will be performed on the scores obtained in the intermediate assessment (initial period) in comparison to the baseline assessment, and the scores obtained in the final assessment in comparison to the intermediate assessment.

For the analysis of the primary endpoint, the instructions described below will be followed:

- Patients with a VKA end date before V1 date: patients who had the Pradaxa® initiation date (the date after VKA end date) within 7 days before V1 date, will be included in the corresponding analyses V1 vs V2 and/or V1 vs V3 and/or V2 vs V3, provided the new visit windows for V2 and/or V3 are met*.
- Patients with Pradaxa® initiation date (the date after VKA end date) = V1 date: all patients will be included in the corresponding analyses (V1 vs V2 and/or V1 vs V3 and/or V2 vs V3), provided the new visit windows for V2 and/or V3 are met*
- Patients with Pradaxa® initiation date (the date after VKA end date) after V1 date: all patients will be included in the corresponding analyses (V1 vs V2 and/or V1 vs V3 and/or V2 vs V3), provided the new visit windows for V2 and/or V3 are met*

* The acceptance windows days for visit 2 and visit 3 will be the following:

- V2 date - Day after VKA end date= 7-124 days
- V3 date - Day after VKA end date= 125-365 days

(NOTE: Due to Pradaxa® initiation date was not recorded in the eCRF, it is assumed that the initiation date of Pradaxa® is the day after the VKA end date)

These analyses will be performed based on the actual anticoagulant treatment received by the patients (i.e. “as-treated” analysis), so that patients who discontinue the initial anticoagulant treatment at the time of an assessment will be excluded from all analyses where data from that assessment is included.

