For the criteria that are not assessable from data reported in the eCRF, patients in whom the investigator indicates criterion non-compliance in the “Selection criteria” section of the eCRF will be excluded.

[figure not shown]
Table 1. Recruited and assessable patients	
n (%)	
Patients recruited	
Non-assessable patients	
Patients who have not granted informed consent in writing prior to enrolment	
Patients under 18 years of age or not diagnosed with NVAf	
Patients who have not been treated continuously with VKAs for stroke prophylaxis for at least six months prior to the baseline visit	
Patients who were not switching to Pradaxa	
Patients receiving Pradaxa® or VKAs for any reason other than stroke prophylaxis in NVAf	
Patients with contraindications for the use of Pradaxa® or VKAs described in the Summary of Product Characteristics (SmPC)	
Patients who are participating in any clinical trial of an investigational medicinal product or medical device	
Assessable patients	
Patients for the safety sample¹	

Note: A single patient may simultaneously be classified as non-assessable for more than one reason.

¹ *All patients participating in the study with follow-up data*

The figure below is a flow diagram of study patients, which will indicate the number of recruited and assessable patients, as well as the number of patients excluded from the study.

Figure 1. Flow diagram of patients

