6.7.1. Adverse reactions to the medication

The table below will describe the data relating to adverse reactions (ARs) to a medication, i.e. AEs associated with the anticoagulant treatment.

Table 56. Adverse reactions to the medication	
	n (%)¹
AVAILABLE PATIENTS ²	
Patients with ARs ³	
Patients with ARs leading to discontinuation of the anticoagulant treatment	
Patients with serious ARs	
Patients without ARs	

¹ All percentages are calculated based on the total number of available patients (n=XX)

² All patients participating in the study with follow-up data

³ A single patient may be classified in both categories: ARs leading to discontinuation of the treatment and serious ARs

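### SAP section 5.2.6 limits its on-treatment safety period by study time only, so events after a patient has stopped Pradaxa can be counted as on-treatment

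*SAP*

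**What the plan says.** SAP section 5.2.6 sets the principle: "The safety analysis will be based on the concept of adverse events that arise during treatment". It then gives the working limits. The events left out are "AEs that appear before the first study visit or after the end of the 7-month follow-up period", where that period is defined as "the 6 months of the study + 30 days follow-up". Such events "will not be deemed to have arisen during treatment and will not be included in the summary tables". No other exclusion is written. The safety sample is equally broad: "The safety analyses will include all patients participating in the study who actually receive follow-up".

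The SAP expects patients to stop Pradaxa. Table 26 has a row for discontinuation during follow-up, Table 56 counts adverse reactions (ARs) that led to stopping, and Table 61 in Annex 2 lists the reasons by visit. For the questionnaire, section 5.2.3 has an as-treated rule: "patients who discontinue the initial anticoagulant treatment at the time of an assessment will be excluded from all analyses" that use data from that assessment. Section 5.2.6 has no counterpart.

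Section 6.7.1 describes ARs as "AEs associated with the anticoagulant treatment", whereas Tables 55, 57 and 58 refer to the study treatment.

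**The concern.** The stated concept is exposure to treatment, but the rule that would be programmed is time in the study. A patient who stops Pradaxa around Visit 2 stays inside the counting window for months. On the written rule, an adverse event, serious adverse event (SAE) or death in those months is not excluded, and so can be tabulated as having arisen on treatment.

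At stake is what the safety tables can be read to mean. A reader would take them to describe events while patients were on Pradaxa. They would in fact describe events on Pradaxa together with events after it, including time on whatever anticoagulant followed, and no row would tell the two apart.

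**Working it through.** The SAP has no figure on this point to reproduce. The check is first one of text, then an illustration of size.

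**Text**
- Start of window (5.2.6): first study visit.
- End of window (5.2.6): six months of study plus 30 days.
- Rule at Pradaxa discontinuation: none in 5.2.6, 6.7 or the footnotes to Tables 55-58.
- Rule at discontinuation for PACT-Q2 (5.2.3): excluded from comparisons that use that assessment.

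The two calendar limits are the only ones given, so a post-stop event inside the window is not removed.

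**Inputs for the illustration**
- Window length: 183 + 30 = 213 days (six months taken as 183 days).
- Pradaxa start is taken as Visit 1, for simplicity.
- Proportion stopping, d: not in the SAP. Assumed 5%, 10% and 20%.
- Stop times: not in the SAP. Assumed uniform over 183 days, mean day 91.5.
- All patients, stoppers included, are assumed to be followed for the full window.

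**Single patient.** Counted off-drug days = 213 − stop day. The last column allows a 30-day lag.

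| Stop day | Off-drug days counted | Share of 213 | Days left after 30-day lag |
|---|---|---|---|
| 30 | 183 | 86% | 153 |
| 91 | 122 | 57% | 92 |
| 180 | 33 | 15% | 3 |

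**Whole sample.** Share of counted person-time off Pradaxa:
- No lag: d × (213 − 91.5)/213 = d × 0.570
- 30-day lag: d × (213 − 91.5 − 30)/213 = d × 0.430

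| d | No lag | 30-day lag |
|---|---|---|
| 5% | 2.9% | 2.1% |
| 10% | 5.7% | 4.3% |
| 20% | 11.4% | 8.6% |

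If stoppers leave follow-up when they stop, these shares fall towards zero. They are shares of person-time. Tables 55-58 report patients as n (%), so no table entry is quantified here. The 30 days is borrowed for illustration only: in the SAP it is follow-up after the study, not after a stop.

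**The case against.** The strongest reply has four parts.

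**The principle may govern.** Section 5.2.6 says which events do not qualify. It does not say that every event inside the window does. It also refers to sponsor standards for adverse-event reporting, which are not shown and may contain an end-of-treatment rule. This is why the claim is that post-stop events can be counted, not that they will be. It does not remove the gap: the explicit rule in the section is the calendar one, and nothing written here overrides it.

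**The tables already separate by association.** Tables 55, 57 and 58 split events by relation to study treatment, the sections on SAEs and deaths say openly that they report events whether or not related, and Table 63 lists event dates. This stands for the associated rows. The total and not-associated rows are still exposed.

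**The AR wording.** A reader might infer from 6.7.1 that a reaction to a later anticoagulant belongs in Table 56. The documents do not support going that far. The text below Table 55, section 6.7.4 and Annex 4 tie ARs to the study treatment, and section 1.10 names only Pradaxa as study medication. What remains is loose wording to harmonise.

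**The denominator.** A reader might also infer that people who never took Pradaxa are in the safety denominator, because the sample requires only follow-up data and Table 1 has a row for "Patients who were not switching to Pradaxa". That row is a non-assessable category, section 5.2.2 bases the analyses on assessable patients, and nothing shows that such patients have follow-up data. The inference is not supported.

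Nor does the contrast with 5.2.3 amount to a contradiction. Counting safety events over study follow-up is an accepted approach, provided that it is labelled as such.

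**Conclusion.** The point holds as a mismatch between the stated concept and the working rule in section 5.2.6. Events after a patient has stopped Pradaxa can enter the safety tables as on-treatment, mainly in the total and not-associated rows of Tables 55, 57 and 58.

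The size is unknown from the SAP. Under 5-20% stopping uniformly over six months with complete follow-up, about 3-11% of counted person-time is off Pradaxa, or about 2-9% once a 30-day lag is allowed. Earlier stops would raise this, and loss of stoppers from follow-up would lower it.

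Severity is minor. The safety analysis is descriptive, no event is lost under the present rule, and the PACT-Q2 analysis is unaffected.

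**What to change.** - **Section 5.2.6:** end each patient's on-treatment period at the recorded Pradaxa stop plus a residual period that the sponsor states for analysis. If no stop date is on file, use the visit at which Pradaxa is recorded as no longer taken, plus the same period.
- **Tables 55-58:** add a row for events after discontinuation, so that later events are shown separately and none are dropped.
- **Sections 5.2.6, 6.7.1 and Table 56:** refer to the study treatment (Pradaxa) throughout the AR wording.

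The cost is SAP wording and a few table rows.

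The downside is precision. Where only a visit date is known, events near the stop are placed approximately. The fallback is weakest for stops first recorded at Visit 3, because section 5.2.3 accepts Visit 3 data up to day 365. With a 30-day residual period, for example, a Visit 3 on day 183 or later gives 183 + 30 = 213, the end of the window, so none of that patient's off-drug time would be moved. The report should state how many stops were dated by visit only.

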1.8. STUDY DESIGN

National, multi-centre, observational study based only on obtaining new data. The study will enrol patients in Spain with NVAf who are treated with VKAs and subsequently start Pradaxa®, and who have given their consent.

Patients will be monitored for a period of six months. Data will be collected at three time points:

1. After the indication for Pradaxa® (baseline period)
2. 30-45 days after starting treatment with Pradaxa® (initial period)
3. 150-210 days after starting treatment with Pradaxa® (continuation period)

The visit windows above for Visit 2 and Visit 3 should be seen as guidance for the treating physician. Visit schedule deviations are expected as the visits are being scheduled according to local clinical routine. For analysis purpose, Visit 2 data that were collected between 7 and 124 days after initiation will be included (rationale for the lower limit is that steady state on Pradaxa® is achieved after 3 days, and first side effects also might occur after a 1st or 2nd intake; rationale for the higher limit is to make sure that there is no overlap with Visit 3). Visit

3 data that were collected between 125 and 365 days after initiation will be included for analysis.

Due to Pradaxa® initiation date was not recorded in the eCRF, it is assumed that the initiation date of Pradaxa® is the day after the VKA end date.

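### Section 5.2.6 starts the during-treatment AE period at the first visit, not at Pradaxa initiation, and gives no rule separating events on VKA after Visit 1

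*SAP*

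**What the plan says.** Section 5.2.6 states the principle: "The safety analysis will be based on the concept of adverse events that arise during treatment". It then sets the time limits: "AEs that appear before the first study visit or after the end of the 7-month follow-up period" are events that "will not be deemed to have arisen during treatment and will not be included in the summary tables". The 7 months are the 6 study months plus 30 days. The safety sample is every participant with follow-up data.

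Section 5.2.3 handles the timing of the switch. Pradaxa initiation was not captured in the eCRF, so it is taken as the day after VKA end, and three cases are distinguished for the PACT-Q2 comparisons:

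- Initiation before V1: "patients who had the Pradaxa® initiation date (the date after VKA end date) within 7 days before V1 date, will be included".
- Initiation on the day of V1: all included.
- Initiation later: "Patients with Pradaxa® initiation date (the date after VKA end date) after V1 date: all patients will be included", with no maximum gap.

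In each case the Visit 2 and Visit 3 windows must also be met. Section 1.8 uses the same assumed initiation date. In justifying the lower limit of the Visit 2 window, it notes that "first side effects also might occur after a 1st or 2nd intake".

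On attribution, section 5.2.6 describes adverse reactions as "AEs related to the anticoagulant treatment", and section 6.7.1 reports "adverse reactions (ARs) to a medication, i.e. AEs associated with the anticoagulant treatment". The introduction to section 6.7 instead ties adverse reactions to the study treatment. Section 1.10 lists only Pradaxa as study medication.

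**The concern.** The stated principle and the operational rule use different time origins. The principle depends on when treatment began; the rule depends on when the first visit took place. The SAP recognises that these dates can differ in either direction and deals with that for the questionnaire, but not for safety.

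What is at stake is how the AR, serious AR, SAE and death frequencies can be read. A reader will take tables labelled with the study treatment as describing the period after the switch to Pradaxa. Under the present rule they may omit recorded events from the first days on Pradaxa, and may include events that occurred on VKA, with nothing in the tables to tell them apart.

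**Working it through.** The SAP gives no figure on this point to reproduce. The check is to set its rules side by side.

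**Inputs**

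- Lower limit of the AE period: V1 (5.2.6).
- Assumed Pradaxa start: VKA end date + 1 day (1.8, 5.2.3).
- Treatment at V1 by design: VKA (3.1).
- Accepted gap when Pradaxa starts before V1: 7 days, for the PACT-Q2 comparisons only (5.2.3).
- Accepted gap when Pradaxa starts after V1: no limit (5.2.3).
- Safety sample: no limit in either direction (5.2.6, footnote to Table 1).

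**Comparison.** Let V1 be day 0 and let the assumed start be day s. The period in 5.2.6 opens on day 0; a period following Pradaxa exposure opens on day s. The two differ as follows:

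- Pradaxa days left outside the period = max(0, −s).
- VKA days from V1 onward not separated from Pradaxa days = max(0, s).

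| s (days from V1) | Source of s | Pradaxa days left out | VKA days not separated |
|---|---|---|---|
| −7 | limit in 5.2.3 | 7 | 0 |
| 0 | case in 5.2.3 | 0 | 0 |
| +14 | assumption | 0 | 14 |
| +30 | assumption | 0 | 30 |

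The last two rows are illustrations; the SAP gives no typical gap after V1.

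**Start before V1.** At s = −7 the excluded days contain the first and second intakes, the very intakes after which section 1.8 says side effects might appear. An AE recorded there occurred on Pradaxa under the SAP's own dating rule, yet 5.2.6 declares it not during treatment. This follows directly from the text.

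**Start after V1.** Nothing in 5.2.6 or section 6.7 says what happens to an AE between V1 and the switch. If adverse reactions are read through the anticoagulant wording (5.2.6, 6.7.1), a VKA reaction in that interval qualifies. If they are read through the study-treatment wording (6.7 introduction, with 1.10), it does not. SAEs and deaths are tabulated whatever their attribution (6.7.2, 6.7.3), so the choice of wording does not settle those counts. None of Tables 55-59 has a row or column for the drug being taken at onset.

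**Partial dates.** Section 6.1.1 accepts VKA dates known only to month and year. A month-only end date leaves 28 to 31 possible initiation dates, one for each day of that month plus one. If V1 falls in that range, the order of V1 and initiation may not be determined. Any rule based on initiation therefore needs a convention for such dates.

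**The case against.** The strongest reply concerns the VKA interval. The V1 sentence in 5.2.6 is an exclusion: it says which events do not count, not that every event after V1 does. If treatment means Pradaxa, an event on VKA already fails the stated principle. If it means anticoagulant treatment in general, counting VKA reactions is intended. This stands in part. A reader might infer that VKA bleeds will be counted as Pradaxa reactions; the SAP does not say so. What it supports is that the term is used in two ways and no rule keeps such events apart. The broader meaning does not rescue V1 as a starting point either, since inclusion criterion 3 requires at least six months of continuous VKA before it.

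A second reply is that V1 may simply be when AE collection began. The study collects only new data, consent precedes enrolment, and 3.1 describes V1 as a time on VKA, so an earlier Pradaxa start is off-design. This also stands in part. Some events before V1 may never have been recorded, and then moving the origin recovers nothing. But the SAP gives no such reason, and non-collection would be a limitation to report, not grounds for declaring on-drug events not during treatment.

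Two stronger readings go too far. One is that an unbounded stretch of Pradaxa exposure is lost in the safety sample. No limit is written for that sample, but nothing in the SAP suggests long gaps before V1. The other is a percentage distortion, for example 30 of about 213 days (roughly 183 + 30), or 14%. The 30-day gap is assumed, and Tables 55-58 count patients rather than exposure time, so that share translates into no reported figure.

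Finally, safety is descriptive and is not among the study objectives in section 3. Table 63 proposes a start date for each listed event, which would allow a later comparison with the VKA end date. That lowers the severity, but it leaves the summary tables as they are.

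**Conclusion.** The point holds in two parts of unequal strength. For patients who started Pradaxa before V1, the rule contradicts the SAP's own principle, and any recorded AE between initiation and V1 is wrongly left out of the summary tables. For patients who started after V1, the defect is one of definition: events on VKA between V1 and the switch can be pooled with Pradaxa events in Tables 55-59, because treatment is defined inconsistently and onset is not split by drug.

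The size is unknown. The SAP gives neither the share of patients in each group nor the number of events, and the only gap it states is the 7 days accepted for the PACT-Q2 comparisons. The conclusion assumes that the day after VKA end is a fair proxy for Pradaxa initiation, as the SAP itself does, and that at least some events in the affected intervals were recorded.

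This should be fixed but is not critical: no primary result changes.

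**What to change.** Amend section 5.2.6 and the shells of Tables 55-59 as follows.

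1. Define the Pradaxa treatment period as starting on the assumed initiation date, the day after VKA end, as in 1.8 and 5.2.3.
2. Count every recorded AE with onset on or after that date, including onset before V1, subject to the existing upper limit.
3. Keep AEs, SAEs and deaths with onset between V1 and initiation in Tables 55-59, but in a separate row or column labelled *on VKA at onset*. Removing them would conflict with 6.7.2 and 6.7.3, which report SAEs and deaths regardless of attribution.
4. Use *study treatment* with one meaning throughout 5.2.6 and 6.7.
5. State a rule for VKA end dates known only to month and year.
6. Report how many patients started Pradaxa before V1 and by how many days, noting that events in that interval may not have been collected.

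The cost is SAP wording, revised table shells and one derived flag from AE start date and VKA end date, with no new data collection and no change to the sample size. The downside is small: some AR and SAE counts will move, and the classification rests on an assumed date that is less certain where the VKA end date is partial.

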6.7. SAFETY ANALYSIS

This section will describe the adverse events reported by patients (see safety sample, Table 1) during the course of the study.

Table 55. Presence of adverse events	
	n (%)
AVAILABLE PATIENTS ¹	
No adverse events	
SERIOUS adverse events	
ASSOCIATED with the study treatment ²	
NOT ASSOCIATED with the study treatment (ARs) ²	
NON-SERIOUS adverse events	
ASSOCIATED with the study treatment ²	
NOT ASSOCIATED with the study treatment (ARs)	

¹ All patients participating in the study with follow-up data

² These AEs will be described in more detail in the following sections

The following sections will describe all the adverse events associated with the study treatment (ARs), as well as the serious adverse events not associated with the study treatment (including deaths).

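### Section 5.2.6 stops counting adverse events at a fixed 7 months although Visit 3 is accepted to day 365, so patients whose only AR or SAE is recorded later are tabulated as event-free

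*SAP*

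**What the plan says.** SAP section 5.2.6 bases the safety analysis on events arising during treatment. Counting starts at the first study visit. Of events that appear "after the end of the 7-month follow-up period (the 6 months of the study + 30 days follow-up"), the section says that they "will not be deemed to have arisen during treatment and will not be included in the summary tables". The SAP does not say from which date the 7 months run.

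Section 1.8 has patients monitored for six months, with days 150-210 as guidance for Visit 3 (V3), and adds: "Visit schedule deviations are expected as the visits are being scheduled according to local clinical routine". For V3, "data that were collected between 125 and 365 days after initiation will be included for analysis". Section 5.2.3 repeats the limit as "V3 date - Day after VKA end date= 125-365 days" and applies an as-treated rule: "patients who discontinue the initial anticoagulant treatment at the time of an assessment will be excluded from all analyses" that use that assessment.

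Section 6.7 introduces the safety tables without a time limit: "This section will describe the adverse events reported by patients (see safety sample, Table 1) during the course of the study". Tables 55 to 58 take as their base all participating patients with follow-up data, however long that follow-up was. Each has a complement row: "No adverse events" in Table 55, patients without ARs in Table 56, patients without SAEs in Table 57 and patients remaining alive in Table 58. No heading or footnote of these tables mentions 7 months. Section 6.7.3 says that Table 58 covers the deaths recorded during the study.

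**The concern.** The safety period fits a V3 held within the guidance window, but not the wider window in which V3 data are accepted. A patient seen late and still on Pradaxa contributes to the V3 comparison of PACT-Q2, while an AR or SAE recorded in the months before that visit is treated as not arising during treatment.

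The event is not merely left out. The patient stays in the denominator and moves to the event-free row, in a table that a reader will take to cover the whole study. For deaths, 5.2.6 and 6.7.3 can be programmed in two ways, and one of them counts a recorded death as a survivor.

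**Working it through.** **Inputs**
- AE period: 6 months + 30 days (5.2.6). The SAP gives no day count; I assume 6 months = 180 to 183 days.
- Accepted V3 window: days 125-365 after assumed initiation, the day after VKA end (1.8, 5.2.3).
- Guidance window for V3: days 150-210 (1.8).
- Initiation relative to Visit 1 (V1): up to 7 days before, the same day, or later with no stated limit (5.2.3).

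**The plan's own figure.** 180 + 30 = 210 = 7 × 30, so the 7 months agree with their stated parts. With 183 days, the cut-off is 183 + 30 = 213.

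**Gap.** Uncounted days before a day-365 V3 = 365 − cut-off, with the cut-off expressed in days after initiation.

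| Anchor of the 7 months | Cut-off (days after initiation) | Gap (days) |
|---|---|---|
| Initiation, or V1 on the same day | 210 to 213 | 365 − 213 = 152 to 365 − 210 = 155 |
| V1, initiation 7 days earlier | 217 to 220 | 365 − 220 = 145 to 365 − 217 = 148 |
| V1, initiation 30 days later (illustrative) | 180 to 183 | 365 − 183 = 182 to 365 − 180 = 185 |

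No choice of anchor shown here closes the gap. With the anchor at initiation, it is 152/365 = 41.6% to 155/365 = 42.5% of the time to a day-365 V3.

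**Where the mismatch begins.** With the anchor at initiation, a V3 by day 210 loses nothing before the visit. The 30 days after the visit are fully covered only for a V3 up to day 210 − 30 = 180 to 213 − 30 = 183.

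**What happens to one patient.** Take an AR on day 250 in a patient on Pradaxa at a V3 on day 300. Day 250 is past day 213, so the AR is left out of Tables 55 to 57. The patient has follow-up data and stays in the base. With no other event, the patient is counted as having no AE and no AR, and as having no SAE if the AR was serious.

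**Check of the date rule proposed below.** Period end = the later of the 7-month limit and V3 + 30 days, with the anchor at initiation.
- V3 on day 170: 170 + 30 = 200, so the end stays at day 210 to 213.
- V3 on day 365: 365 + 30 = 395.
- AR on day 230, Pradaxa stopped for it on day 240, V3 on day 300: the end is day 330 and the AR is counted. If the extension applied only to patients still on Pradaxa at V3, this AR would be lost, although ARs leading to discontinuation are a parameter that 5.2.6 names.
- Spread of period ends for a V3 within day 365: 395 − 213 = 182 to 395 − 210 = 185 days.

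**The case against.** A fixed window is a recognised choice for crude percentages without person-time. It treats all patients alike, and 6 months + 30 days matches the six months of monitoring in section 1.8. The text says that late events are not deemed to arise during treatment, which is a counting convention and not a factual claim. Being on Pradaxa at V3 does not prove unbroken exposure either, since Table 59 has an action code for stopping and reintroducing. The introductory wording of 6.7 and 6.7.3 is general and can be read as subject to 5.2.6. The exclusion names only the summary tables, so the individual listing in Annex 8.4 may still show late events.

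Most of this stands as a defence of having a fixed window. It does not defend an unlabelled one, because the tables carry complement rows and nothing tells the reader that they stop at 7 months. If Annex 8.4 does list the late events, it will disagree with Tables 55 to 59 without explanation.

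Two stronger readings are tempting. A reader might infer that the safety tables will materially understate harm. The SAP gives neither a distribution of V3 dates nor an event rate, so that cannot be shown. A reader might also infer that the safety section was overlooked when the visit windows were revised. Section 5.2.1 has blank entries, so its silence on 5.2.6 is not evidence.

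**Conclusion.** The point holds as an inconsistency in counting and labelling. Followed as written, 5.2.6 places patients whose only recorded AR or SAE is late in the event-free rows of Tables 55 to 57. If the cut-off is carried into Table 58, it does the same for late deaths, against 6.7.3.

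The uncounted stretch before a day-365 V3 is at most 152-155 days with the anchor at initiation and 145-148 days with the anchor at V1 and initiation 7 days earlier. It is longer if initiation follows V1. These figures rest on 6 months being 180-183 days. They measure the time that can go uncounted in one patient, not the share of patients affected, which is unknown and may be small. Safety reporting is descriptive and the PACT-Q2 analysis is unaffected, so the change is worth making but is not critical.

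**What to change.** In section 5.2.6:
- State the date from which the 7 months run.
- End each patient's AE period at the later of the existing 7-month limit and the actual V3 date plus the existing 30 days. Apply this to every patient in the safety sample with a V3, whatever the Pradaxa status at that visit; the present limit does not depend on status either. Patients without a V3 keep the 7-month limit.

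In the tables:
- Use this period in Tables 55 to 57 and 59, and report follow-up time beside the crude percentages.
- Reconcile 5.2.6 with 6.7.3 by counting all recorded deaths in Table 58 and flagging those outside the period.
- If a fixed window is also kept, label it as within 7 months and give later ARs, SAEs and deaths on a separate line.

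No event counted today is lost. The cost is SAP wording and a changed date filter, using dates already in the plan: V3 and VKA end date (5.2.3) and AE start date (Table 63). The downside is unequal follow-up. Period ends differ by up to about 182-185 days for a V3 within day 365 with the anchor at initiation, and by more for a later V3, because the safety sample is not limited to in-window visits. Reported counts may rise slightly.
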